the Columbia-Suicide Severity Rating Scale (C-SSRS) at all visits.⁵⁴⁻⁵⁵ A participant will be referred to a mental health provider (MHP) or primary care provider if the participant has a PHQ-9 score of ≥ 15 , any suicidal behavior, or any suicidal ideation of type 4 or 5 on the C-SSRS and a member of the study team may contact a participant's existing mental health provider if a participant presents with acute suicidal ideation/behavior at a study visit. The decision as to whether the participant will be allowed to continue in the trial will be made by the local medical monitor ([name]) in consultation with the MHP or primary care provider after the referral clinical visit. Participants who already have an existing mental health provider and/or are followed by their primary care provider for mental health will have their mental health provider and/or primary care provider alerted if the participant has a PHQ-9 score of ≥ 15 or any suicidal behavior or suicidal ideation of type 4 or 5 on the C-SSRS.

Eating disorders will be evaluated using the eating disorder examination-questionnaire (EDE-Q).⁴⁶ Any participant endorsing vomiting, laxative use, and/or diuretic use for weight control (via the EDE-Q by standard scoring procedures), will be interviewed by a pediatric behavioral psychologist using the Eating Disorders Module of the Structured Clinical Interview for Diagnostic and Statistical Manual of Mental Disorders, 5th Edition (DSM-5). If disordered eating is present upon clinical interview, the participant will be removed from the study and referred to an eating behavior specialist for clinical follow-up. If no eating disorder is present, the participant may continue in the study.

5.3 Study Duration:

14 weeks, including 2 weeks of topiramate titration up to 75 mg daily (or maximum tolerated dose; as described in **Section 4.1**) followed by 12 weeks on topiramate.

5.4 Use of radiation:

The iDXA consists of exposure to 0.01 mSv. In comparison, a resident of the State of Minnesota receives approximately 3 mSv from natural background radiation as a result of living in Minnesota. There are no other sources of radiation in this study.

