- Current or recent (< 6 months prior to enrollment) use of long-acting stimulant medications, **unless** participant has been on stable doses of such medication for \geq 6 months. In terms of short-acting ADHD stimulant medications, the PI will determine eligibility based on weight and dose (no studies have shown this contributes to weight outcomes).
- Baseline bicarbonate $<$ 18 mmol/L
- Baseline creatinine $>$ 1.2 mg/dL
- Females: pregnant, planning to become pregnant, or, if sexually active, unwilling to use 2+ acceptable contraceptive methods during the study period

8.3 Screening:

Patients seen in the University of Minnesota PWMCs who are deemed appropriate candidates to receive topiramate (without contraindications) for weight loss by an obesity medicine specialist will be referred for this study.

Screening/Baseline Visit (Visit 1):

Participants will be asked to present at this visit after having fasted for \geq 12 hours. At this visit, the participant's parent/legal guardian will be taken through the consent process and will sign the parental consent form, and the participant will be asked to sign the assent form, after all have had the opportunity to learn about the study and ask any questions they may have. The participant will then undergo the following:

- Review of inclusion/exclusion criteria
- Demographics including age, sex, self-reported race/ethnicity, home address, total family combined income, parents' level of education and employment status
- Physical exam and tanner stage. The physical examination will not need to be repeated if performed by a CPOM faculty member, pediatric weight management provider, and/or pediatric endocrinologist within the last 30 days before Screening/Baseline visit. A trained professional can perform the Tanner staging.
- BMI/Anthropometrics: height, weight, waist and hip circumference, and BMI
- Blood pressure and heart rate
- Pregnancy test for females
- Contraceptive counseling
- Review of medications
- Blood draw for safety labs (creatinine and bicarbonate) and cardiometabolic risk labs (lipids, glucose, insulin, and A1c)
- Genotyping (via saliva collection)
- iDXA (body composition)
- Bioelectrical impedance analysis (via Tanita Scale)
- Eating behavior and physical activity questionnaires (hunger/satiety visual analog scales, AEBQ, FCQ-T-r, dYFAS, RED-5, BEVQ-15, PAQ-A)
- Safety questionnaire for eating disorders (EDE-Q)

MEDICAL PROTOCOL (HRP-590)

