12.0 Withdrawal of Participants

12.1 Withdrawal Circumstances:

Participants will be allowed to withdraw from the study at any time. Those who wish to withdraw may notify the research team in writing or by telephone. Participants may also be withdrawn from the study at any time based upon investigator judgement. Finally, in the event that a participant has a serious adverse event that is deemed related to the study medication and/or procedures by either the external or internal medical monitor ([name] and [name], respectively), the participant will be required to immediately discontinue the intervention.

12.2 Withdrawal Procedures:

As it is generally recommended that patients choosing to discontinue topiramate be weaned off of this medication, we will recommend for any participant choosing to withdraw from the study, or being withdrawn as described above, the following weaning schedule (consistent with clinical practice in the PWMC):

- Take 50 mg daily for one week, followed by:
- Take 25 mg daily for one week, and then discontinue.

In the event of an emergent medical situation, it may be recommended to cease topiramate without tapering the dose. For those participants that choose to withdraw, we will not plan to collect any additional data beyond that point, as the primary data of import in this study is topiramate concentration levels.

12.3 Termination Procedures:

It will be noted in the participant enrollment log that the participant has discontinued the study, and the date of the last study related visit. No additional data will be collected after that time. Data that has already been collected can be used in the study analysis.

Given the pragmatic nature of this study, including the fact that most participants recruited will be from our PWMCs and will continue to be followed through our PWMCs (if they so desire) after their participation in this study has terminated, many participants completing this study may continue to take topiramate after study completion. In that case, per usual clinical practice the medication will be prescribed by the participant's PWMC provider. For those not yet followed in the PWMC who are interested in continuing topiramate and/or being followed in our clinics, appointments in the PWMC will be established for continuation of topiramate and ongoing clinical management. All additional follow up in the PWMC will continue as per usual clinical

MEDICAL PROTOCOL (HRP-590)

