PROTOCOL TITLE: Pharmacokinetics and Pharmacodynamics of Topiramate for Weight Loss in Youth: PHARMATOP

VERSION DATE: 05/03/2024

practice. If a participant elects to discontinue topiramate after study completion, we will use the same withdrawal procedure as described in **Section 12.2**, and additional topiramate will be provided by the IDS for this purpose.

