taste), fatigue, dizziness, somnolence, nervousness, psychomotor slowing, difficulty with memory and/or concentration/attention, cognitive problems, confusion, mood problems, fever, infection, and flushing. In our experience, the most common side effect is transient irritability and rarely do patients discontinue topiramate due to side effects. Of note, we will be following generative verbal fluency during the study with the COWA test and working memory via the NIH-TB List Sorting Working Memory Test and Pattern Comparison Processing Speed Test. According to the package insert, the following additional adverse reactions to topiramate have been identified:

- Acute myopia and secondary angle closure glaucoma
- Oligohidrosis and hyperthermia
- Metabolic acidosis
- Suicidal behavior and ideation. Participants who have active suicidal ideation will be referred to their own mental health provider, have a mental health referral generated or be referred to the emergency department.
- Fetal toxicity
- Kidney stones
- Seizure precipitation with sudden withdrawal
- Hyperammonemia and encephalopathy
- Hypothermia

13.2 Reproduction Risks:

Topiramate can cause fetal harm in pregnant women. Available data indicate an increased risk in oral clefts (cleft lip with or without cleft palate) with first trimester exposure to topiramate. When multiple species of pregnant animals received topiramate at clinically relevant doses, structural malformations, including craniofacial defects, and reduced fetal weights occurred in offspring. Therefore, all female participants who are sexually active must agree to use two forms of birth control during their time in the study. Females of childbearing potential will have pregnancy tests at baseline/screening (during which visit they also complete the iDXA scan) and at the Week 6, Week 10 and Week 14 visits. Urine pregnancy tests will be used as often as possible, but a serum pregnancy test may also be conducted. If a patient becomes pregnant while taking topiramate, treatment will be discontinued immediately and the patient will be apprised of the potential hazard to a fetus again at that time.

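### The contraception commitment and new-event capture end with the study, but the protocol's own taper can add up to 14 more days of topiramate

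*Combined protocol and SAP*

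**What the plan says.** **Contraception.** Section 8.2 excludes a female who is, "if sexually active, unwilling to use 2+ acceptable contraceptive methods during the study period". Section 13.2 says sexually active females "must agree to use two forms of birth control during their time in the study". Section 5.2 also asks for confirmation of two methods and gives no end date.

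**Length of study.** Section 5.3 gives "14 weeks, including 2 weeks of topiramate titration up to 75 mg daily" or the maximum tolerated dose, and then 12 weeks on drug. It mentions no taper.

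**Taper.** Section 12.2 states: "we will recommend for any participant choosing to withdraw from the study, or being withdrawn as described above, the following weaning schedule". The schedule is one week at 50 mg, and then "Take 25 mg daily for one week, and then discontinue". An emergency may justify stopping without it. For completers who decide to stop, section 12.3 says "we will use the same withdrawal procedure as described in" section 12.2, and that the investigational pharmacy will supply the extra drug.

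**Data collection.** For participants who choose to withdraw, section 12.2 says "we will not plan to collect any additional data beyond that point". For anyone logged as having discontinued the study, section 12.3 says "No additional data will be collected after that time". Section 13.7 records events that begin between consent and the final day of participation, and follows events already recorded until they resolve or stabilize.

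**The concern.** The protections are tied to the study calendar, while the risk follows the drug. Section 13.2 warns of fetal harm and of more oral clefts after first-trimester exposure. A participant who tapers is still taking topiramate, on the protocol's advice or from its pharmacy. By then the two-method commitment has ended and no contact is planned that would bring a new event or a pregnancy to light.

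The plan handles the same doses differently on the way up. Titration through 25 mg and 50 mg counts as study time and has a side-effect call at Week 2. The step-down through the same doses has neither.

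What is at stake is participant safety and the completeness of the safety record. The popPK model, the exposure-response analysis and the sample size are untouched.

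**Working it through.** No power or error-rate formula applies. The check is day and dose arithmetic, plus a comparison of the windows.

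**Inputs**
- Study: 2 weeks of titration plus 12 weeks (section 5.3).
- Titration: 25 mg for one week, 50 mg for one week, then 75 mg (section 4.1).
- Taper: 50 mg for one week, 25 mg for one week (section 12.2).
- Side-effect reviews: Weeks 2, 4, 6, 8, 10 and 14 (Table 1).
- Pregnancy tests: baseline and Weeks 6, 10 and 14 (section 13.2).
- Visit window: ±7 days (section 8.3).
- Planned enrollment 65; drop-out 25% assumed, 10–15% usual (section 15.2).

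**Stated duration.** 2 + 12 = 14 weeks = 98 days. This reproduces section 5.3 and leaves no days for a taper.

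**Length and dose of the taper**
- Days: 7 + 7 = 14.
- Dose: 7 × 50 + 7 × 25 = 525 mg.
- Titration for comparison: 7 × 25 + 7 × 50 = 525 mg over 14 days, all inside the 14 weeks.

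**Completer on 75 mg who stops, with full adherence**
- Last dose at about day 98 + 14 = 112. With the Week 14 visit at day 91 to 105, the range is day 105 to 119.
- Share of days on drug: 14 / 112 = 12.5%.
- Share of dose: 525 / (525 + 84 × 75 + 525) = 525 / 7,350 = 7.1%.

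**Participant held at 50 mg.** If the taper starts one step below the current dose (an assumption), it is 7 days and 7 × 25 = 175 mg.

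**Scheduled contacts**

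| | Weeks 0–14 | Taper |
|---|---|---|
| Side-effect reviews after baseline | 6 | 0 |
| Pregnancy tests | 4 | 0 |

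**How many withdraw.** 0.10 × 65 = 6.5; 0.15 × 65 = 9.75; 0.25 × 65 = 16.25. That is about 7 to 16 participants of both sexes, or 7 to 10 at the usual rate. Even this is an upper range, since some will already be off drug or out of contact. The documents do not say how many completers will stop, or how many sexually active females will taper.

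**Do the windows reach the taper?**
- *Completers who stop:* section 12.3 itself places their taper after study completion, so it lies outside all three windows (contraception, new-event recording, scheduled tests).
- *Withdrawers:* the answer depends on what counts as the final day of participation, which is not defined. The data stops in sections 12.2 and 12.3 both point to the discontinuation date.
- No section carries contraception, pregnancy testing or new-event capture through to the last dose.

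**The case against.** The best case against the point has five parts.

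1. *Undefined terms and missing forms.* No section defines the study period or the end of participation, and section 5.3 does not set out to fix a contraception window. The consent and assent forms are not in this copy and may already cover the taper. This stands as a limit: the point concerns the protocol text only.

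2. *Withdrawers are less clear than completers.* The data stop in section 12.2 covers only those who choose to leave. After a related serious event, sections 12.1 and 18.2 end the intervention without saying that participation ends the same day. The taper is only recommended to withdrawers, as usual clinic practice, and pharmacy supply is stated only for completers. This narrows the point, but the stop in section 12.3 is not limited to voluntary withdrawal.

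3. *The pregnancy-test contrast is weak.* In-study gaps between tests are 6, 4 and 4 weeks, and titration has no test before Week 6. Fourteen days without a test is shorter than any of these. That is right, so the point rests on the commitment and on event capture, not on a missing test.

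4. *Partial protections exist.* These are contraceptive counseling at baseline; the open-ended wording in section 5.2; the Week 14 exam, test and side-effect review; the section 13.2 rule to stop drug if pregnancy occurs on topiramate; and the section 13.7 five-day notice of unanticipated problems, which has no onset cutoff. Many participants also stay in clinic care. But the last two rules act only if the team learns of an event, and nothing is scheduled to find one. Clinic follow-up is optional.

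5. *The size is small.* By dose the share is 7.1%, at falling doses, and few participants are likely to be affected. This is accepted.

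**Conclusion.** The point holds. As written, the plan lets the contraception commitment and routine new-event capture lapse while some participants still take topiramate under its own taper. The uncovered exposure is at most 14 days and 525 mg. For a completer who stops, that is 12.5% of days on drug and 7.1% of the dose.

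The gap is plain for completers who stop and probable for withdrawers. Completers who continue topiramate under a clinic prescription are outside it.

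The conclusion assumes that the study period means the 14 weeks of section 5.3, that withdrawal ends participation, that the taper is taken in full, and that the consent forms add nothing further. The numbers affected cannot be derived from the documents, and the contraception part probably concerns few. It is a safety improvement that should be made, with no bearing on power or the primary analysis.

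**What to change.** - **Sections 8.2 and 13.2:** replace the study-period wording with *through the last dose of topiramate taken under this protocol, including any taper*.
- **Sections 12.2, 12.3 and 13.7:** exempt adverse-event and pregnancy follow-up from the stop on data collection, and record events with onset up to that last dose.
- **One phone call at the end of the taper**, where the participant agrees, on side effects, pregnancy and whether the taper was completed. The Week 2 and Week 4 calls are a ready template.

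The documents give no half-life, so any margin beyond the last dose would be an added assumption and is not proposed here.

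The cost is a few sentences in five sections and one call per participant who stops. If the consent and assent texts do not already say this, they need matching, including the Spanish parental consent. Some withdrawers will decline the call.

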9.0 Vulnerable Populations

9.1 Vulnerable Populations:

Population / Group	Identify whether any of the following populations will be targeted, included (not necessarily targeted) or excluded from participation in the study.
Children	Targeted Population
Pregnant women/fetuses/neonates	Excluded from Participation
Prisoners	Excluded from Participation
Adults lacking capacity to consent and/or adults with diminished capacity to consent, including, but	Excluded from Participation

MEDICAL PROTOCOL (HRP-590)

PROTOCOL TITLE: Pharmacokinetics and Pharmacodynamics of Topiramate for Weight Loss in Youth: PHARMATOP

VERSION DATE: 05/03/2024

not limited to, those with acute medical conditions, psychiatric disorders, neurologic disorders, developmental disorders, and behavioral disorders	
Non-English speakers	Included/Allowed to Participate
Those unable to read (illiterate)	Excluded from Participation
Employees of the researcher	Excluded from Participation
Students of the researcher	Excluded from Participation
Undervalued or disenfranchised social group	Included/Allowed to Participate
Active members of the military (service members), DoD personnel (including civilian employees)	Excluded from Participation
Individual or group that is approached for participation in research during a stressful situation such as emergency room setting, childbirth (labor), etc.	Excluded from Participation
Individual or group that is disadvantaged in the distribution of social goods and services such as income, housing, or healthcare.	Included/Allowed to Participate
Individual or group with a serious health condition for which there are no satisfactory standard treatments.	Included/Allowed to Participate
Individual or group with a fear of negative consequences for not participating in the research (e.g. institutionalization, deportation, disclosure of stigmatizing behavior).	Excluded from Participation
Any other circumstance/dynamic that could increase vulnerability to	Excluded from Participation

MEDICAL PROTOCOL (HRP-590)

PROTOCOL TITLE: Pharmacokinetics and Pharmacodynamics of Topiramate for Weight Loss in Youth: PHARMATOP

VERSION DATE: 05/03/2024

coercion or exploitation that might influence consent to research or decision to continue in research.	
--	--

9.2 Additional Safeguards:

At least one parent signature is required for permission for a minor to enroll in the study. Children ages 8 to <18 years old will be asked to document their agreement by signing an assent form. The research will not involve wards of the state or any other agency, institution, or entity. All consent and assent will be documented.

It is possible that the parent of a child may not be comfortable with reading and speaking English and would prefer that the consent be available in Spanish. For that reason, we have had the parental consent translated into Spanish. As most of the children we encounter are comfortable with speaking and reading English, we will not be translating the assent form at this time. We have two native Spanish speakers on our team who can help with answering questions that might arise with the parent at visits.

10.0 Local Number of Participants

10.1 Local Number of Participants to be Consented:

All participants will be consented locally. The approximate number of participants we plan to enroll is 65. The lowest number that will allow for data analysis is 40, and the maximum that might agree to participate is 80.

11.0 Local Recruitment Methods

11.1 Recruitment Process:

One of the primary strengths of this study is its pragmatic nature. Our 3.5-month duration (2 weeks to increase topiramate to maximum dose, followed by 3 months on this dose) for this study was chosen because the FDA, as well as most obesity management guidelines,¹⁻³ recommend that pharmacotherapies used for obesity treatment either be altered or discontinued after 3 months if response is insufficient. For example, the FDA recommends that for adults on the combination of phentermine 7.5 mg/topiramate 46 mg daily, if weight loss is <5% at 3 months, then the dose should be titrated up to the maximum-strength dose of phentermine 15 mg/topiramate 92 mg daily. Most patients prescribed an anti-obesity medication are, therefore, generally on the medication for at least 3 months on the same dose assuming they do not develop adverse effects to the treatment. In this sense, this study largely entails the addition of measures including anthropometrics (e.g. height, weight, BMI), blood draws, and questionnaires onto routine clinical care being performed in our and other weight management clinics. We believe that this will substantially facilitate recruitment for our study.

At the Center for Pediatric Obesity Medicine (CPOM), we have strong recruitment infrastructure. For this study, participants will primarily be recruited directly from our PWMCs by providers and support staff within the clinics. Additional participants may be recruited among those who contact CPOM (after receiving recruitment letters for CPOM studies), are interested in

MEDICAL PROTOCOL (HRP-590)

PROTOCOL TITLE: Pharmacokinetics and Pharmacodynamics of Topiramate for Weight Loss in Youth: PHARMATOP

VERSION DATE: 05/03/2024

participating in a study that specifically involves the initiation of an active anti-obesity pharmacotherapy at study onset (versus possibility of receiving a placebo), and who qualify (meet inclusion/exclusion criteria). Inclusion in the study will be determined by the enrollment criteria. There is a vast number of potentially eligible participants. Our PWMCs generally have $\geq 3,000$ patient visits per year, a number that is continuing to rise with the recent expansion of our clinical capacity and volume (four new obesity medicine specialists hired in the last few years; seven total obesity medicine providers). Further, ≥ 500 youth to date have been prescribed topiramate through our clinics and, with our recent clinical expansion, this number is expected to continue to substantially grow. Given our clinical volume and our established recruitment infrastructure, we do not anticipate problems with recruiting the cohort during the study duration.

If recruitment is below target for any reason, we can utilize partner institutions within the Minnesota Pediatric Obesity Consortium (MN-POC) for assistance with recruitment. Member institutions of MN-POC include the University of Minnesota, Mayo Clinic, Children's Hospitals and Clinics of Minnesota, and Park Nicollet/Health Partners, collectively representing a large portion of the pediatric medical care provided in the state of Minnesota. All MN-POC institutions are within reasonable driving distance of the University of Minnesota, and most refer patients to our PWMCs for obesity management already.

11.2 Identification of Potential Participants:

From the PWMC, youth with severe obesity will be identified by PWMC providers as appropriate candidates to receive topiramate. The study PI ([name]) is a PWMC provider and is, therefore, in regular communication with other PWMC providers. Additional participants may be recruited among those who contact CPOM (after receiving recruitment letters for CPOM studies), are interested in participating in a study that specifically involves the initiation of an active anti-obesity pharmacotherapy at study onset (versus possibility of receiving a placebo), and who qualify (meet inclusion/exclusion criteria). After identification, potential participants will be given an IRB-approved recruitment letter about the project. Interested participants will be asked to contact the study team, and up to five follow-up phone calls will be made by study staff if the potential participant leaves a message. Further, with verbal parental permission, PWMC providers will also contact the study team about potential participants identified. The only information provided to the study team prior to official enrollment will include name and contact information.

11.3 Recruitment Materials:

Recruitment letters will be created for this study and approved by the IRB before use. Appropriately certified staff within the PWMC may approach potential participants and speak to them about the study and provide them with a flyer with a QR code that connects them to the research coordinator and indicates a preferred method of communication (email, phone or text).

11.4 Payment:

While this study is largely pragmatic in nature in the sense that it largely entails the addition of measures including anthropometrics, blood draws, and questionnaires onto routine clinical care being performed in PWMCs, we still recognize the additional commitment needed from the

MEDICAL PROTOCOL (HRP-590)

PROTOCOL TITLE: Pharmacokinetics and Pharmacodynamics of Topiramate for Weight Loss in Youth: PHARMATOP

VERSION DATE: 05/03/2024

participant and family members. Therefore, the children who participate in this study will receive payment for the visits they complete. Payments will be made by the Greenphire ClinCard.

- Screening/baseline visit: \$50
- Week 6 visit: \$35
- Week 8 visit (blood draw only): \$25
- Week 10 visit: \$40
- Week 14 visit: \$50
- Return of electronic prescription bottle (Visit 14): \$25
- Total: \$225

